### **11.3.3 Phase Ib**

Standard single 12-lead ECGs (with a 10-second rhythm strip) will be collected at screening, Cycle 1 Day 1 (prior to first dose), Cycle 2 Day 1 (prior to the respective PK sample collection), and at the end of treatment. ECGs should be collected after the patient has rested quietly and is awake in a fully supine (or semi-recumbent, if supine is not tolerated) position for 5 to 10 minutes and prior to any blood draw collection.

## **11.4 PHARMACOKINETIC MEASUREMENTS**

### **11.4.1 Phase Ia**

Blood samples for full PK profile analysis of GDC-0810 (and its acyl-glucuronide and N-glucuronide metabolites) will be collected on Day -7 at 0 (predose), 0.5, 1, 1.5, 2, 3, 4, 6, 8, 24 (Day -6), and 48 (Day -5) hours postdose. A second set will be collected on Day 29 (Cycle 2 Day 1) at 0 (predose), 0.5, 1, 1.5, 2, 3, 4, 6, 8, and 24 hours postdose (Cycle 2 Day 2, prior to the next dose).

### **11.4.2 Phase IIa**

Blood samples for determining trough PK (predose) concentrations of GDC-0810 will be collected in Cycles 1, 2, 3 and 4.

Additionally, on Cycle 2 Day 1, PK samples will also be collected predose and at 1, 2, 3, 4, 6 hours following dosing. If PK sampling times coincide with ECG collection times, the ECGs have to be assessed prior to PK blood collection.

### **11.4.3 Phase Ib**

For Cohort C1, on Cycle 1 Day 1 and Cycle 1 Day 8, PK samples will be collected predose and at 1, 2, 3, 4, and 6 hours following dosing to measure the concentrations of GDC-0810 and palbociclib. Additionally, blood samples for determining trough PK (predose) concentrations of GDC-0810 and palbociclib will be collected on Day 1 in Cycles 2, 3, 4, and *at end of treatment*.

For Cohort D1, on Cycle 1 Day 1 and Cycle 2 Day 1, PK samples will be collected predose and at 1, 2, 3, 4, and 6 hours following dosing to measure the concentrations of GDC-0810 and LHRH agonists. If PK sampling times coincide with ECG collection times, the ECGs have to be assessed prior to PK blood collection. Additionally, blood samples for determining trough PK (pre-dose) concentrations of GDC-0810 and LHRH agonists will be collected on Day 1 in Cycles 3, 4, and *at end of treatment*.

See the Laboratory Manual for collection and processing procedures.

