## 2.2 CLINICAL OVERVIEW OF PALBOCICLIB

Palbociclib is being evaluated in many cancer types including breast, ovarian, gastrointestinal stromal tumors (GIST), liposarcomas, acute leukemias, and mantle cell lymphomas.

The DLT of palbociclib is reversible myelosuppression, specifically reversible neutropenia (Gr 1–2: 33–54%; Gr 3–4: 20–50%). Other hematological toxicities include thrombocytopenia (Gr 1–2: 7–58%; Gr 3–4: 0–17%) and anemia (Gr 1–2: 20–64%; Gr 3–4: 2–17%). Phase I and II clinical trials demonstrate that palbociclib is a well-tolerated agent with mild to moderate fatigue (10–34%), nausea (24–30%), and diarrhea (1–30%) as the most commonly reported non-hematological adverse reactions (Schwartz et al. 2011; Flaherty et al. 2012; Dickson et al. 2013; Vaughn et al. 2015). Grade 3 and Grade 4 febrile neutropenia occurred in one of 30 patients (3%) in the two single-agent Phase II studies, respectively (Dickson et al. 2013; Vaughn et al. 2015).

The PALOMA-1 Phase II study randomized women with advanced ER+ human epidermal growth factor 2 (HER2-) breast cancer who had not received any systemic

treatment for their advanced disease to receive either letrozole 2.5 mg QD alone or with palbociclib 125 mg QD administered daily for 21 days followed by a seven day off-period (21/7). The most common adverse events reported for the palbociclib plus letrozole group were neutropenia (74%), leukopenia (43%), fatigue (40%), anemia (35%), and nausea (25%). Grade 3 treatment-related adverse events (AEs) reported in  $\geq 20\%$  of patients were neutropenia (48%) and leukopenia (19%). There were no cases of febrile neutropenia reported. The most frequently reported Grade 4 adverse events were neutropenia (6%), pulmonary embolism (5%), and fatigue (2%). The results showed substantial efficacy with the palbociclib and letrozole combination by significant improvement in median progression-free survival of 20 months (95% CI: 13.8, 27.5 months) compared to letrozole alone (10.2 months; 95% CI: 5.7, 12.6 months) ([Finn et al. 2009](#)). Palbociclib received accelerated approval from the United States Food and Drug Administration (FDA) in 2015.

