#### Phase Ib

- To evaluate the pharmacokinetics of GDC-0810 in combination with palbociclib and/or an LHRH agonist.
- To evaluate the pharmacokinetics of palbociclib and/or an LHRH agonist in combination with GDC-0810

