### **Continuous Dosing**

In Phase Ib, GDC-0810 will be given continuously beginning on Cycle 1 Day 1 in 28-day cycles. During Cycle 1 of the dose escalation, patients will return to the clinic on a weekly basis (Days 8, 15, and 22) for safety evaluation and collection of predose PK samples. On those days, treatment will be administered in the clinic. Study treatments, palbociclib will be given on Days 1–21 of each cycle and LHRH agonist will be given on Day 1 of each cycle. Evening dosing (*within 30 minutes after dinner or within 30 minutes of the consistently largest meal of the day*) may be initiated to alleviate gastrointestinal symptoms from GDC-0810. However, on Day 28 of Cycles 1, 2, and 3, the dose of GDC-0810 should be taken in the morning to allow trough PK sample collections on Cycle 2 Day 1, Cycle 3 Day 1, and Cycle 4 Day 1.

Similarly, on Day 1 of every subsequent new cycle of dosing beginning with Cycle 2, study treatment will be administered in the clinic following all the assessments as indicated in the Schedule of Activities.

All other doses of GDC-0810 or palbociclib will be administered on an outpatient basis. It is anticipated that some patients may occasionally forget to take a dose of GDC-0810 or palbociclib. In those cases, patients should just take the next scheduled dose, without compensating for the missed dose.

*Palbociclib and GDC-0810 do not have to be taken together; however, each drug should be taken at a consistent time each day.*

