**Table 6 Dose Modification Guidelines for Hematologic Toxicities**

Toxicity	Palbociclib	GDC-0810
Neutropenia or thrombocytopenia Grade $\leq 2$	No dose modification required.	No dose modification required.
Uncomplicated Grade 3 neutropenia	Withhold palbociclib until recovery to Grade $\leq 2$ ( $\geq 1000/\text{mm}^3$ ). No dose adjustment is required unless recovery of neutrophil count is delayed a,b , in which case reduce by one dose level.	No dose modification required.
Uncomplicated Grade 4 neutropenia (ANC $< 500/\text{mm}^3$ )	Withhold palbociclib until recovery to Grade $\leq 2$ ( $\geq 1000/\text{mm}^3$ ). Resume at next lower dose. Reduce by two dose levels c if neutrophil recovery is delayed a or in case of recurrent Grade 4 event.	No dose modification required.
Grade $\geq 3$ neutropenia associated with infection or fever	Withhold palbociclib until neutrophil count recovery to Grade $\leq 2$ ( $\geq 1000/\text{mm}^3$ ) and afebrile and infection is clinically improving. Resume palbociclib at next lower dose. Reduce by two dose levels c if neutrophil recovery is delayed a . In case of Grade 4 febrile neutropenia, discuss with Medical Monitor prior to resuming palbociclib.	No dose modification required.
Uncomplicated Grade $\geq 3$ thrombocytopenia (platelet count $< 50,000/\text{mm}^3$ )	Withhold palbociclib until recovery to Grade $\leq 2$ ( $\geq 50,000/\text{mm}^3$ ). Resume at next lower dose. Reduce by two dose levels c if platelet count recovery is delayed a or in case of recurrent Grade 4 event.	No dose modification required.

ANC=absolute neutrophil count.

a If recovery of neutrophils to  $\geq 1000/\text{mm}^3$  or platelet count to  $\geq 50,000/\text{mm}^3$  takes  $> 2$  weeks (including dose holding due to toxicity, the scheduled week off treatment, or  $> 7$  days of cycle delay).

b If uncomplicated Grade 3 neutropenia recurs in 2 consecutive cycles, after recovery as per retreatment criteria (ANC  $\geq 1000/\text{mm}^3$  and no fever), treatment may restart at the next lower dose level at investigator's discretion.

c If no further dose reduction is possible (i.e. patient is already receiving 75 mg/day according to the 3/1 schedule), consider changing the schedule to 75 mg/day, 2 weeks on/2 weeks off, or discontinue palbociclib and continue with GDC-0810 alone.

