### **15.4 PHARMACOKINETIC ANALYSES**

For PK analyses, the analysis population will consist of the subset of treated patients who have at least one PK sample collected.

During the Phase Ia *portion of the study*, full plasma PK profiles will be obtained for GDC-0810 and its glucuronide metabolites, and analyzed using non-compartmental methods for all patients in the dose escalation portion of the study.

In the Phase IIa portion of the study, full plasma PK profiles will be obtained for GDC-0810 and analyzed using non-compartmental methods.

In the Phase Ib portion of the study, full plasma PK profiles will be obtained for GDC-0810 and palbociclib and/or LHRH agonists and analyzed using non-compartmental methods.

In addition, in the Phase Ia/IIa/Ib, blood samples for determination of the steady-state trough concentrations (predose) of GDC-0810 will be *obtained from* all patients.

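### Palbociclib samples on Day 1 of Cycles 2 to 4 come after the scheduled week off, so they are washout concentrations, not the troughs that Section 11.4.3 calls them

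*Combined protocol and SAP*

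**What the plan says.** Section 11.4.3 sets two kinds of PK sample for Cohort C1, each for both drugs. The first is serial: "on Cycle 1 Day 1 and Cycle 1 Day 8, PK samples will be collected predose" and then at 1, 2, 3, 4 and 6 hours. The second is a single predose sample: "blood samples for determining trough PK (predose) concentrations of GDC-0810 and palbociclib will be collected on Day 1 in Cycles 2, 3, 4", and again at end of treatment.

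The two drugs have different schedules. GDC-0810 runs without a break, while Section 10.3.3 states that "palbociclib will be given on Days 1–21 of each cycle". Section 2.2 describes the 21/7 regimen as including seven days off, and the footnote to Table 6 on delayed recovery counts time "including dose holding due to toxicity, the scheduled week off treatment".

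The related Phase Ib secondary objective in Section 6.2 is "To evaluate the pharmacokinetics of palbociclib and/or an LHRH agonist in combination with GDC-0810". Section 15.4 says that "full plasma PK profiles will be obtained for GDC-0810 and palbociclib and/or LHRH agonists and analyzed using non-compartmental methods". Its later sentence on steady-state troughs names GDC-0810 alone.

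Two further places do not fit with the rest:
- The List of Abbreviations and the Table 2 footnote gloss 21/7 as Days 1–21 of 28, yet add that there is no dosing holiday.
- Section 10.3.3 has predose PK collected at the Cycle 1 visits on Days 8, 15 and 22. The Appendix 3 grid shows no PK sample on Day 15 or Day 22.

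**The concern.** Day 1 of the next cycle suits GDC-0810, and Section 10.3.3 prepares for it by asking for a morning GDC-0810 dose on Day 28. No palbociclib dose falls on Day 28. The sampling day of a continuously dosed drug has been applied to an intermittently dosed one, and both results carry the same label.

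If the palbociclib values were tabulated under that label, exposure in the combination would look far lower than it is. The direction matters. Section 10.4.3 describes GDC-0810 as a weak CYP3A inhibitor and palbociclib as cleared mainly by CYP3A and SULT2A1, although it rates the interaction risk as low. Any such interaction would raise palbociclib exposure, and washout values read as troughs would point the other way. Section 10.1.3.1 also has PK data reviewed before escalation decisions.

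**Working it through.** The plan states no palbociclib trough, half-life or expected concentration, so there is no figure of its own to reproduce. The formulas below assume mono-exponential decline. As a check on that simplification, Section 1.2 gives GDC-0810 a half-life of about 8 h. Once-daily accumulation is then 1/(1 − 2^(−24/8)) = 1.14, which agrees with the minimal accumulation reported there.

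**Inputs**
- Last palbociclib dose of a cycle: Day 21 (Section 10.3.3).
- Next Day 1 predose sample: Day 29 of a 28-day cycle (Section 11.4.3).
- Palbociclib half-life t: not in the documents; assumed 12 to 72 h.
- Cohort C1: 4 patients on 9 September 2016, median treatment duration 134 days, range 56–138 (Section 1.1).

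**Step 1: time since last dose.** (29 − 21) × 24 = 192 h with no cycle delay. A once-daily trough is at 24 h, so the excess is 192 − 24 = 168 h. A cycle delay, or a palbociclib hold late in the 21 days, lengthens it.

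**Step 2: Day 1 value as a share of a 24-h trough.** R = 2^(−168/t).

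**Step 3: Cycle 1 Day 8 predose as a share of the steady-state trough.** After 7 daily doses, F = 1 − (2^(−24/t))^7 = 1 − 2^(−168/t). The exponent is the same, so F = 1 − R. The last column therefore also shows by how much a Day 1 value would understate a 24-h trough.

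| Assumed half-life | R: Cycle 2–4 Day 1 | F: Cycle 1 Day 8 predose |
|---|---|---|
| 12 h | 0.006% | over 99.9% |
| 24 h | 0.8% | 99.2% |
| 36 h | 3.9% | 96.1% |
| 48 h | 8.8% | 91.2% |
| 72 h | 19.8% | 80.2% |

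**Step 4: number of samples.** The ceiling is 4 × 3 = 12. Day 1 of Cycles 2, 3 and 4 falls on Days 29, 57 and 85. With four patients the median is the mean of the two middle durations, so these sum to 2 × 134 = 268. Neither exceeds 138, so the smaller is at least 268 − 138 = 130. Three patients had therefore passed Day 85, and the fourth, at 56 days, had not reached Day 57. That is 3 × 3 + 1 = 10 sampling days reached at that cut, if no cycle was delayed. The documents do not say how many samples were drawn.

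**Step 5: Cycle 1 visits in dispute.** A Day 15 predose sample, or a Day 22 sample, would be about 24 h after the Day 14 or Day 21 dose. Either would be a genuine on-treatment trough if it was taken, which Section 10.3.3 implies and Appendix 3 does not.

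**The case against.** The strongest reply is that little depends on the label. The objective is general and names no trough. Serial sampling on Cycle 1 Days 1 and 8 takes place while palbociclib is being dosed, and Section 15.4 rests the palbociclib analysis on profiles. No palbociclib trough summary is planned there. Section 15.1 makes all analyses descriptive, and no cohort receives palbociclib alone for comparison. Enrollment has stopped, and most of these samples had probably been drawn.

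Most of this stands, and it rules out three stronger readings.
- A reader might infer that the palbociclib PK objective cannot be met. The serial samples still address it, and the Day 8 predose value is close to steady state over most of the assumed range.
- A reader might infer that Day 8 is the only on-treatment multiple-dose predose sample. Section 10.3.3 also mentions Days 15 and 22, so that point is unresolved.
- A reader might infer that the plan will report a false interaction. Nothing in Section 15.4 specifies a palbociclib trough summary or such a comparison.

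The reply does not rescue the label. Section 11.4.3 states the purpose of these samples as trough determination for palbociclib, and Section 15.4 is silent on their handling, so nothing stops them from being summarised that way. The remark that 21/7 has no dosing holiday does not help either: the same gloss gives Days 1–21 of 28, which is the basis of the 192 h.

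**Conclusion.** The point holds as a labelling and analysis error. For palbociclib, the Day 1 samples in Cycles 2 to 4 are taken 192 h after the last dose and represent washout. Under mono-exponential decline and an assumed half-life of 12 to 72 h, they are about 0.006% to 20% of a 24-h trough. The 192 h depends only on the stated dosing days and the absence of a cycle delay; the percentages depend on the assumed half-life.

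What is lost is repeat on-treatment trough data after Cycle 1. The consequence is small: one cohort of 4 patients, at most 3 such samples each, a secondary objective and descriptive reporting. The end-of-treatment sample has a related weakness, because its time since the last palbociclib dose is not fixed.

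**What to change.** Change the wording of Sections 11.4.3 and 15.4 as follows:
- Describe the palbociclib results from Day 1 of Cycles 2 to 4 as post-break (washout) concentrations. Keep the trough label on those days for GDC-0810.
- Report each with the actual time since the last palbociclib dose, and do the same for the end-of-treatment sample.
- Exclude the Day 1 values from any palbociclib trough or steady-state summary.
- Use the Cycle 1 Day 8 predose value as the on-treatment palbociclib trough.

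Three sets of passages must be reconciled:
- Section 10.3.3 and Appendix 3 on predose PK at Cycle 1 Days 15 and 22. Any such samples taken should be reported as on-treatment troughs.
- The remark in the List of Abbreviations and Table 2 that 21/7 has no dosing holiday, against Sections 2.2 and 10.3.3 and Table 6.
- The Appendix 3 footnotes that place the clinic-day dose before any assessment, against those that require predose samples. The Day 8 value depends on this order.

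The cost is wording and fewer values labelled as palbociclib trough. It needs no patient, visit or blood draw. Where the last palbociclib dose time is not already in the data, a site query would be needed. No redraw at Cycle 2 Day 15 is proposed: Appendix 3 has only a blood count there, and most patients had passed that visit by the September 2016 cut.

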## 11.5 CORRELATIVE STUDIES

### 11.5.1 FES-PET

Imaging with FES-PET will be performed to quantify ER expression in the tumor and to assess for PD response to GDC-0810 therapy. While FES uptake can vary between patients, in general, the FES uptake is fairly consistent across lesions at a given timepoint, and the average uptake provides a reasonable summary of ER expression for an individual patient (Kurland et al. 2011). Factors that can affect standardized uptake value, such as sex hormone-binding globulin (SHBG), will be adjusted as per standard protocol (Peterson et al. 2011). In addition, a washout period for patients previously treated with tamoxifen (at least 2 months), fulvestrant (at least 6 months), or other hormonal therapy (at least 2 weeks) will be required due to the long half-life of each drug and its potential to interfere with FES uptake. FES-PET studies will be performed as hybrid PET/CT imaging for attenuation correction and lesion localization. FES-PET scan is not required for patients enrolled in Phase Ib.

#### 11.5.1.1 Phase Ia

During dose escalation, pre- and post-treatment functional ER imaging with FES-PET/CT scans will be performed starting at dose level 2 (200 mg) at screening (baseline) and at 4 weeks of treatment (Cycle 2 Day 3), as per [Table 7](#):

**Table 7 Pre- and Post-Treatment Functional ER Imaging with FES-PET/CT Schedule (Phase Ia)**

Cycle 2 Day 1	PK sampling day at 0 (predose) to 8 hours postdose as per protocol Section 11.4.1
Cycle 2 Day 2	No GDC-0810 dose prior to clinic visit 24-hr PK sample Take GDC-0810 dose in the evening that day (please see below instructions for fasting before and after)
Cycle 2 Day 3	FES-PET scan during the period between <math>\geq 18</math> and <math>\leq 24</math> hours post the evening dose on C2D2 No GDC-0810 dose on this day
Cycle 2 Day 4	Resume daily dosing of GDC-0810 in the morning as per protocol Section 10.3.1
Cycle 2 Day 8 (<math>\pm 1</math> day)	Optional biopsy as per protocol Section 11.5.2.1 below
Cycle 3 (~same day as CT/MRI scans)	FES-PET scan during the period between $\geq 2$ and $\leq 12$ hours post the morning dose Only necessary if Cycle 2 Day 3 scan shows incomplete pharmacodynamic activity of GDC-0810

For more details:

Cycle 2 Day 2: After the 24-hour postdose PK sample is collected (Section 11.4.1), the patient will be instructed to take her next dose of GDC-0810 at home that evening at 6:00 p.m.  $\pm$  1 hour, observing a fasting period of at least 4 to 6 hours predose and 1 hour of fasting postdose, followed by dinner. For example, start fasting after *completion of* lunch at 12:00 noon, take the dose of GDC-0810 at 6:00 p.m., followed by dinner at 7:00 p.m.

Cycle 2 Day 3: Without taking another dose of GDC-0810 in the morning, the FES-PET/CT scan should be performed during the period between  $\geq$ 18 and  $\leq$ 24 hours after the evening dose administered on Cycle 2 Day 2. Following the same example above, the scan should be performed between 12:00 noon and 6:00 p.m. No dose of GDC-0810 will be administered on this day.

Cycle 2 Day 4: Resume daily dosing of GDC-0810 in the morning, after fasting overnight; food should not be eaten for at least 1 hour after taking GDC-0810.

Cycle 3: Only necessary if the Cycle 2 Day 3 scan shows incomplete PD activity of GDC-0810: a repeat FES-PET/CT scan will be performed on the same day as the Cycle 3 CT/MRI tumor evaluation scans during the period between  $\geq$ 2 and  $\leq$ 12 hours postdose (administered that morning at the normal time).

If low FES uptake is observed at baseline, the investigator will determine whether the post-treatment scans are warranted.

#### 11.5.1.2 Phase IIa

During Phase IIa, pre- and post-treatment functional ER imaging with FES-PET/CT scans will be performed in all Cohort A1 patients at screening (baseline) and at Cycle 3, as per Table 8:

[figure not shown]
**Table 8 Pre- and Post-Treatment Functional ER Imaging with FES-PET/CT Schedule (Phase IIa)**

COHORT A1 ONLY	
Cycle 3 Day 1	Perform all routine labs as per protocol Section 11.2, including ECG assessments
Cycle 3 Day 2	Take GDC-0810 dose in the evening this day
Cycle 3 Day 3	No GDC-0810 dose on this day Perform FES-PET scan during the period between <math>\geq</math>18 and <math>\leq</math>24 hours post the evening dose on C3D2
Cycle 3 Day 4	Resume normal GDC-0810 dosing
Cycle 3 Day 8 ( $\pm$ 1 day)	Biopsy as per protocol Section 11.5.2.2 below (Patients in Cohort A2 can have the biopsy any time during Cycle 3)

In addition, if feasible, a FES-PET/CT scan should also be performed at the time when disease progression is suspected (especially if disease progression occurs prior to Cycle 3).

### **11.5.2 Tumor Biopsies**

Pre- and post-treatment tumor biopsies from the same (whenever feasible) soft tissue or visceral metastatic lesion will be collected to evaluate the histology of the tumor versus stroma, to assess for ER degradation and PR protein levels (via IHC), PR downregulation, proliferative index (Ki67), and ER target gene modulation studies. Tumor biopsies will also be used for DNA and /or RNA extraction to enable next generation sequencing (NGS) *and/ or whole genome sequencing (WGS)* for exploratory research on biomarkers (including, but not limited to, cancer-related genes and biomarkers associated with common molecular pathways).

#### **11.5.2.1 Phase Ia**

Optional tumor biopsies will be collected predose and after 4 weeks of treatment (Cycle 2 Day  $8 \pm 1$  day, during the period between  $\geq 2$  and  $\leq 12$  hours postdose). This schedule will allow the patient to have resumed daily morning dosing of GDC-0810 for at least 3 days since the FES-PET/CT scan was performed.

#### **11.5.2.2 Phase IIa**

All Cohort A patients with safely accessible soft tissue and/or visceral metastases will be required to have tumor biopsies. Optional tumor biopsies will be collected for Cohort B patients with safely accessible soft tissue and/or visceral metastases. Biopsies should be performed predose, at Cycle 3 (Day  $8 \pm 1$  day for patients in Cohort A1), and if feasible, at the time when disease progression is suspected (especially if disease progression occurs prior to Cycle 3). Biopsies should be collected during the period between  $\geq 2$  and  $\leq 12$  hours postdose.

